CRF	Case Report/Record Form (paper or electronic)
CRO	Contract Research Organization
CSR	Clinical Study Report
DSM-5	Diagnostic and Statistical Manual of Mental Disorders, Fifth Edition
eCRF	electronic Case Report Form
EDC	Electronic Data Capture
FDA	Food and Drug Administration
GCP	Good Clinical Practice
ICF	Informed Consent Form
ICH	International Conference on Harmonization of Technical Requirements for Registration of Pharmaceuticals for Human Use
IEC	Independent Ethics Committee
IRB	Institutional Review Board
IRT	Interactive Response Technology Corporate Confidential Information
ISMT	Illness Self-Management Training
ISST-Plus	InterSePT Scale for Suicidal Thinking-Plus
MAP-SR	Motivation and Pleasure-Self Report
MedDRA	Medical dictionary for regulatory activities
MMRM	Mixed-effects model for repeated measures
PANSS	Positive and Negative Syndrome Scale
PDT	Prescription Digital Therapeutic
PRO	Patient Reported Outcomes
SAE	Serious Adverse Event
SCID	Structured Clinical Interview for DSM-5
SD	standard deviation
SST	Social Skills Training
SOM	Site Operations Manual
SUSAR	Suspected Unexpected Serious Adverse Reactions
WHO	World Health Organization
WHOQOL-BREF	World Health Organization Quality of Life

Glossary of terms

Additional treatment	Medicinal products that may be used during the clinical trial as described in the protocol, but not as an investigational medicinal product (e.g. any background therapy)
Assessment	A procedure used to generate data required by the study
Biologic Samples	A biological specimen including, for example, blood (plasma, serum), saliva, tissue, urine, stool, etc. taken from a study subject
Cohort	A specific group of subjects fulfilling certain criteria and generally treated at the same time
Electronic Data Capture (EDC)	Electronic data capture (EDC) is the electronic acquisition of clinical study data using data collection systems, such as Web-based applications, interactive voice response systems and clinical laboratory interfaces. EDC includes the use of Electronic Case Report Forms (eCRFs) which are used to capture data transcribed from paper source forms used at the point of care.
End of the clinical trial	The end of the clinical trial is defined as the last visit of the last subject or at a later point in time as defined by the protocol.
Enrollment	Point/time of subject entry into the study at which informed consent must be obtained
Mis-randomized subjects	Mis-randomized subjects are those who were not qualified for randomization and who did not take study treatment, but have been inadvertently randomized into the study
Other treatment	Treatment that may be needed/allowed during the conduct of the study (concomitant or rescue therapy)
Part	A sub-division of a study used to evaluate specific objectives or contain different populations. For example, one study could contain a single dose part and a multiple dose part, or a part in subjects with established disease and in those with newly-diagnosed disease.
Patient	An individual with the condition of interest for the study
Period	The subdivisions of the trial design (e.g. Screening, Treatment, Follow-up) which are described in the Protocol. Periods define the study phases and will be used in clinical trial database setup and eventually in analysis
Personal data	Subject information collected by the Investigator that is transferred to Novartis for the purpose of the clinical trial. This data includes subject identifier information, study information and biological samples.
Premature subject withdrawal	Point/time when the subject exits from the study prior to the planned completion of all study treatment administration and/or assessments; at this time all study treatment administration is discontinued and no further assessments are planned
Randomization number	A unique identifier assigned to each randomized subject
Screen Failure	A subject who did not meet one or more criteria that were required for participation in the study

Source Data/Document	Source data refers to the initial record, document, or primary location from where data comes. The data source can be a database, a dataset, a spreadsheet or even hard-coded data, such as paper or eSource.
Start of the clinical trial	The start of the clinical trial is defined as the signature of the informed consent by the first subject.
Study treatment	Any single drug or combination of drugs or intervention administered to the subject as part of the required study procedures.
Study treatment discontinuation	When the subject permanently stops taking any of the study treatments prior to the defined study treatment completion date (if any) for any reason; may or may not also be the point/time of study discontinuation
Subject	A trial participant (can be a healthy volunteer or a patient)
Subject number	A unique number assigned to each subject upon signing the informed consent. This number is the definitive, unique identifier for the subject and should be used to identify the subject throughout the study for all data collected, sample labels, etc.
Treatment arm/group	A treatment arm/group defines the dose and regimen or the combination, and may consist of 1 or more cohorts.
Variable	A measured value or assessed response that is determined from specific assessments and used in data analysis to evaluate the treatment being tested in the study
Withdrawal of study consent	Withdrawal of consent from the study occurs only when a subject does not want to participate in the study any longer, and does not allow any further collection of personal data.

Corporate Confidential Information

Protocol summary

Protocol number	CPEA001A12201
Full Title	A Randomized, Sham-Controlled Study of PEAR-004 as an adjunct to standard-of-care treatment for schizophrenia
Brief title	Study of efficacy of PEAR-004 in schizophrenia
Sponsor and Clinical Phase	Novartis Phase II
Investigation type	Device
Study type	Interventional
Purpose and rationale	
The purpose of the study is to determine in patients currently being administered antipsychotic pharmacotherapy whether PEAR-004 can further reduce symptoms of schizophrenia as measured by the Positive and Negative Syndrome Scale (PANSS).
 
The overall rationale for the study is to assess the first prescription digital therapeutic (PDT) in schizophrenia using a form of proven psychosocial intervention, cognitive behavioral therapy (CBT), to supplement standard of care with antipsychotic medications.

Primary Objective(s)	The primary objectives are to assess the efficacy of PEAR-004 as an adjunct to existing clinician-directed pharmacotherapy to reduce symptoms of schizophrenia by change in total PANSS score, and to evaluate retention to assigned study treatment by percent dropout rate at the end of the study
Secondary Objectives	
Objective 1: To evaluate the efficacy of PEAR-004 as an adjunct to existing clinician-directed pharmacotherapy to reduce positive symptoms of schizophrenia by change in Positive and General Psychopathology PANSS scores
 
Objective 2: To evaluate the efficacy of PEAR-004 as an adjunct to existing clinician-directed pharmacotherapy to reduce negative symptoms of schizophrenia by change in Negative PANSS score and Motivation and Pleasure-Self Report (MAP-SR) score
 
Objective 3: To assess safety and tolerability of PEAR-004 by adverse event monitoring and InterSePT Scale for Suicidal Thinking-Plus (ISST-Plus) score
 
Objective 4: To evaluate the efficacy of PEAR-004 as an adjunct to existing clinician-directed pharmacotherapy to improve psychosocial functioning in patients with schizophrenia by change in World Health Organization Quality of Life (WHOQOL-BREF) scale
 
Objective 5: To evaluate the efficacy of PEAR-004 as an adjunct to existing clinician-directed pharmacotherapy to reduce depression symptoms in patients with schizophrenia by change in Beck Depression Inventory, Second Edition (BDI-II) score
 
Objective 6: To evaluate the magnitude of the effect of PEAR-004 as an adjunct to existing clinician-directed pharmacotherapy to reduce symptoms of schizophrenia by percentage improvement in PANSS score
 
Objective 7: To evaluate the response to treatment by the proportion of responders

	Objective 8: To evaluate patient adherence to antipsychotic medication by change in Brief Medication Questionnaire (BMQ)
Study design	This is a randomized, sham controlled, rater-blinded, parallel group trial. Patients will be randomized 1:1 to receive PEAR-004 or a sham control. The study includes an up to 4-week screening period, a 12-week treatment period, and a 4-week follow-up period.
Population	The study will enroll approximately 102 male and female adults (18-65 years of age, inclusive) with a diagnosis of schizophrenia
Key Inclusion criteria	
 • Signed informed consent must be obtained prior to participation in the study. • Healthy male and female subjects 18 to 65 years of age, inclusive, and in good health as determined by medical history, physical examination, and vital signs at screening • SCID-based Diagnostic and Statistical Manual of Mental Disorders, Fifth Edition (DSM-5) diagnosis of schizophrenia and a total PANSS score > 60 • Proficient in English at 5th grade reading level or higher, in the judgement of the investigator • Capable of using a mobile device (compatible with PEAR-004) and using common applications, in the judgement of the investigator
Key Exclusion criteria	
 • Major change in primary antipsychotic medication in the prior 4 weeks before screening (e.g., switching to a new agent or a major dose adjustment within two weeks of randomization) • Planning to move out of the geographic area within 3 months • Unable to use English to participate in the consent process, the interventions or assessments • Inability to comply with study procedures, due to severe medical conditions or otherwise • Meet DSM-5 diagnosis for a current episode of major depression, mania, or hypomania in the past month • Meet DSM-5 diagnosis for a current moderate or severe alcohol or cannabis use disorder in the past 2 months • Meet DSM-5 diagnosis for a current substance use disorder (other than alcohol or cannabis) in the past 2 months • Considered high risk for suicidal behavior based on ISST-Plus score at screening, in the judgement of the investigator • Previously participated in a clinical study involving PEAR-004
Study treatment	PEAR-004 Sham control
Efficacy assessments	
 • PANSS • BMQ • MAP-SR • WHOQOL-BREF • BDI-II
Key safety assessments	
 • Adverse event monitoring • Vital signs • ISST-Plus

Other assessments	Corporate Confidential Information
Data analysis	
The change from baseline in total PANSS score will be analyzed using the mixed-effects model for repeated measures (MMRM), with fixed, categorical effects of treatment, visit, and treatment-by-visit interaction, as well as the continuous, fixed covariates of baseline score, baseline score-by-visit interaction, and disease duration at baseline. An unstructured covariance structure will be used to model the within-patient errors. The Kenward-Roger method will be used to adjust the estimated covariance of the mean difference and the degrees of freedom. Several other covariance structures will be tested if there are convergence issues in the primary analysis.
 
The primary hypothesis to be tested is that mean change from baseline in PANSS is greater with PEAR-004 than with Sham at day 85 or last visit. The primary comparison will be the contrast between treatments on day 85. The significance test will be carried out using 1-sided $\alpha=0.05$. In addition, two-sided 90% confidence intervals for the treatment mean differences, as well as individual treatment mean change from baseline values at each study visit will be constructed.
 
Two sensitivity analyses (the selection model and the pattern mixture model) will be performed to assess the robustness of the primary analysis to missing data results. The LOCF approach will also be performed to aid in the interpretation of the results from the primary analysis.

Key words	Schizophrenia, prescription digital therapeutic, cognitive behavioral therapy, smartphone app

1 Introduction

1.1 Background

Schizophrenia is a common condition occurring in about 1% of the general population [Saha et al 2005](#). It is treated with antipsychotic medications, which can help acute exacerbations of delusions or hallucinations, but do not improve the long-term course of the illness. Functional impairment is severe and disabling, and not improved by medication. Most patients are unable to work or live independently.

Cognitive-behavioral therapy (CBT) has been shown to improve symptoms of schizophrenia somewhat, both for delusions and hallucinations (“positive” symptoms) as well as for apathy and flat affect (“negative” symptoms) and functional status (engagement with employment or social interactions) [Rector and Beck 2001](#). Access to CBT can be difficult based on cost and availability of psychotherapists. PEAR-004 is being developed as a prescription digital therapeutic (PDT), delivered via mobile devices, that delivers coping skills from evidence-based treatments such as CBT, Social Skills Training (STS), and Illness Self-Management Training (ISMT). It is intended to be used by patients who are under the care of a qualified healthcare professional and are on antipsychotic pharmacotherapy. If efficacious, it would demonstrate that 24/7 access to evidence-based coping skills, which when added to medications, may improve symptom management and functional outcomes.

PEAR-004 is intended to deliver multimodal evidence-based neurobehavioral mechanisms of action which include Cognitive Restructuring, Behavioral Activation, ISMT, and SST. Preliminary evidence has shown that patients with psychotic disorders can actively engage with software similar to PEAR-004, which suggests that PEAR-004 may improve both positive and depressive symptoms in patients with schizophrenia [Ben-Zeev et al 2014](#); [Ben-Zeev et al 2016](#) and serious mental illness [Ben-Zeev et al 2018](#).

PEAR-004 is comprised of a patient-facing mobile-device application interface (via smartphone) and a clinician-facing web interface. The patient application delivers therapeutic content organized into multiple domains representing common symptoms or problem areas for patients with schizophrenia including: thoughts, voices, social functioning, medication, mood, sleep, and other coping skills for daily life. Patients are prompted to interact with PEAR-004 three times per day by automated notifications. Therapeutic content is delivered via a series of short interactions. Patients can select a therapeutic domain and choose what kind of skill they think would be most helpful. Patients then choose the specific skill and have the option of watching, reading, or listening to content about what the skill is and how they can give it a try. Patients then view tips for successful practice, and after they practice a skill are asked to provide feedback about whether the skill was helpful. Helpful skills are stored in the Toolbox to promote repeated practice and skill mastery.

PEAR-004’s academic precursor is FOCUS, a software-based intervention (delivered via mobile devices) designed with input from both treatment providers and patients to optimize both usability and engagement and developed to be used in conjunction with ongoing outpatient treatment [Ben-Zeev et al 2013](#). The feasibility, acceptability, and initial efficacy of FOCUS for improving symptoms and treatment engagement in patients with schizophrenia was established in a one month open-label trial. In this trial, overall satisfaction (91%), retention (100%), and

engagement (patients active 87.5% of trial days) were very high. Participants in this trial had significant reductions in both overall symptoms of schizophrenia and depression from baseline to end of trial [Ben-Zeev et al 2014](#).

In a separate study [Ben-Zeev et al 2016](#), engagement with FOCUS among patients with schizophrenia was measured during a 6-month period following psychiatric hospitalization discharge. Similar to findings from the one-month feasibility trial, patients with schizophrenia were highly engaged over the course of 6 months (active use on 82% of the weeks during which they had access to the intervention). Taken together, these preliminary findings show the promise of PEAR-004 (developed based on the academic version of FOCUS software) as a PDT for improving symptoms and treatment outcomes in patients with schizophrenia.

1.2 Purpose

The purpose of the study is to determine in patients currently being administered antipsychotic pharmacotherapy whether PEAR-004 can further reduce symptoms of schizophrenia as measured by the total score on the Positive and Negative Syndrome Scale (PANSS).

2 Objectives and endpoints

Table 2-1 Objectives and related endpoints

Objectives and endpoints	
Primary Objective	
Objective	Endpoint

 To assess the efficacy of PEAR-004 as an adjunct to existing clinician-directed pharmacotherapy to reduce symptoms of schizophrenia 	
 Change in total PANSS score from baseline to day 85 or last visit

 To evaluate retention to assigned study treatment 	
 Percent dropout rate
Secondary Objectives	
Objectives	Endpoints

 To evaluate the efficacy of PEAR-004 as an adjunct to existing clinician-directed pharmacotherapy to reduce positive symptoms of schizophrenia 	
 Change in the Positive PANSS score from baseline to day 29, day 57, and day 85 or last visit Change in the General Psychopathology PANSS score from baseline to day 29, day 57 and day 85 or last visit

 To evaluate the efficacy of PEAR-004 as an adjunct to existing clinician-directed pharmacotherapy to reduce negative symptoms of schizophrenia 	
 Change in the Negative PANSS score from baseline to day 29, day 57, and day 85 or last visit Change in the Motivation and Pleasure self-report (MAP-SR) score from baseline to day 29, day 57, and day 85 or last visit

 To assess safety and tolerability of PEAR-004 	
 Adverse events, serious adverse events, and adverse events leading to discontinuation throughout the study

	
 • Vital signs at baseline, day 85 or last visit • InterSePT Scale for Suicidal Thinking-Plus (ISST-Plus) score at baseline, day 29, day 57, day 85, and day 115 or last visit

 • To evaluate the efficacy of PEAR-004 as an adjunct to existing clinician-directed pharmacotherapy to improve psychosocial functioning in patients with schizophrenia 	
 • Change on the World Health Organization Quality of Life (WHOQOL-BREF) scale from baseline to day 29, day 57, and day 85 or last visit

 • To evaluate the efficacy of PEAR-004 as an adjunct to existing clinician-directed pharmacotherapy to reduce depression symptoms in patients with schizophrenia 	
 • Change in the Beck Depression Inventory, Second Edition (BDI-II) total score from baseline to day 29, day 57, and day 85 or last visit

 • To evaluate the magnitude of the effect of PEAR-004 as an adjunct to existing clinician-directed pharmacotherapy to reduce symptoms of schizophrenia 	
 • Percentage change in PANSS score (within assigned group) from baseline to day 29, day 57, and day 85 or last visit

 • To evaluate the response to treatment 	
 • Proportion of responders, defined as a reduction of at least 20% at day 85 or last visit in total PANSS score relative to baseline

 • To evaluate patient adherence to antipsychotic medication 	
 • Change in antipsychotic pharmacotherapy use as measured by the Brief Medication Questionnaire (BMQ) at day 29, day 57, and day 85 or last visit

Exploratory Objectives

Corporate Confidential Information

Corporate Confidential Information

3 Study design

This is a randomized, sham controlled, rater-blinded, parallel group trial. Approximately 102 subjects will be randomized 1:1 in to the following groups:

- Group A: Clinician-directed pharmacotherapy + PEAR-004
- Group B: Clinician-directed pharmacotherapy + Sham application

An up to 28-day screening period will include standard screening assessments as defined in the assessment schedule. Eligible subjects will be randomized on day 1 into one of the treatment groups.

Subjects in both groups will continue to receive their clinician-directed standard of care treatment for schizophrenia, including pharmacotherapy. Subjects in Group A will use PEAR-004 for a period of 12 weeks. Subjects in Group B will use a sham for a period of 12 weeks. Subjects will return to the clinic for outpatient visits at week 4 (day 29), week 8 (day 57), and week 12 (day 85). At each visit, standard assessments will be performed according to the assessment schedule, including PANSS, ISST-Plus, CGI, BMQ, MAP-SR, WHOQOL-BREF, BDI-II, ISI, and Adverse Events (AEs). A final follow-up visit will be performed at week 16 (day 115), including the assessments as detailed in the assessment schedule.

Figure 3-1 Study Design

4 Rationale

The overall rationale for the study is to assess the first PDT in schizophrenia using evidence-based coping skills to supplement standard of care with antipsychotic medications.

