Subjects should be seen for all visits/assessments as outlined in the Assessment schedule ([Table 8-1](#)) or as close to the designated day as possible. Missed or rescheduled visits should not lead to automatic discontinuation. Subjects who prematurely discontinue the study for any reason should be scheduled for a visit as soon as possible, at which time all of the assessments listed for the final visit will be performed. At this final visit the adverse event and concomitant medications should be recorded on the CRF.

Table 8-1 Assessment Schedule

Epochs	SCREENING (Non-Treatment)	Treatment				EOS
Visit Name	Screening	Treatment				EOS
Weeks		1	4	8	12	16
Days	-28 to -1	1	29	57	85	115
Obtain informed consent	X					
Corporate Confidential Information						
Inclusion /Exclusion criteria	S					
Relevant med history / current medical conditions	X					
Demography	X					
Physical examination	S					S*
Randomization		X				
PEAR-004/Sham distribution and data collection ¹		X	X	X	X	X
Corporate Confidential Information						
Body height	X					
Body weight	X	X ³				X*
Vital signs (Body temp, blood pressure, pulse rate)	X	X ³			X	X*
Concomitant meds/Therapies	X	X	X	X	X	X*
PANSS	X	X ³	X	X	X	X*
ISST-Plus	X	X ³	X	X	X	X*
Corporate Confidential Information						
BMQ		X ³	X	X	X	X*
MAP-SR		X ³	X	X	X	X*
WHOQOL-BREF		X ³	X	X	X	X*
BDI-II		X ³	X	X	X	X*
Corporate Confidential Information						

Epochs	SCREENING (Non-Treatment)	Treatment				EOS
Visit Name	Screening	Treatment				EOS
Weeks		1	4	8	12	16
Days	-28 to -1	1	29	57	85	115
Adverse Events	X	X	X	X	X	X
Serious Adverse Events	X	X	X	X	X	X

Note: If several assessments are scheduled at the same time point, please see the SOM for guidance on recommended sequence of assessments

X = assessment to be recorded in clinical database

S = assessment to be recorded in source documentation only and will not be entered into the CRF

*These assessments are also to be conducted for subjects who discontinue study treatment

¹ Data collection from day 1 through day 85.

Corporate Confidential Information

³ Assessment performed on day 1 prior to PEAR-004/Sham distribution is considered baseline.

Corporate Confidential Information

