9.1 Discontinuation

9.1.1 Discontinuation of study treatment

Discontinuation of study treatment for a subject occurs when study treatment is stopped earlier than the protocol planned duration, and can be initiated by either the subject or the investigator.

The investigator must discontinue study treatment for a given subject if, he/she believes that continuation would negatively impact the subject's well-being.

- Study treatment must be discontinued if the subject withdraws consent.

If discontinuation of study treatment occurs, the investigator should make a reasonable effort to understand the primary reason for the subject's premature discontinuation of study treatment and record this information.

Subjects who discontinue study treatment or who decide they do not wish to participate in the study further should NOT be considered withdrawn from the study UNLESS they withdraw their consent (see withdraw of informed consent section.). **Where possible, they should return for the assessments indicated** in the Assessment schedule (Table 8-1), especially the day 85 and EOS (day 115) visits. If they fail to return for these assessments for unknown reasons, every effort (e.g. telephone, e-mail, letter) should be made to contact the subject/pre-designated contact as specified in the lost to follow-up section. This contact should preferably be done according to the study visit schedule.

If the subject cannot or is unwilling to attend any visit(s), the site staff should maintain regular telephone contact with the subject, or with a person pre-designated by the subject. This telephone contact should preferably be done according to the study visit schedule.

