12.4.3 Handling of missing values/censoring/discontinuations

The primary MMRM model implicitly imputes missing data under a missing at random (MAR) assumption. Therefore, no explicit imputation of missing data will be done for the primary analysis approach.

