12.4.4.2 Supportive analyses

The last-observation-carried-forward (LOCF) approach will be applied to analyze the change from baseline in the total PANSS score. These results will only be used to aid in the interpretation of the results from the primary analysis.

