
depression symptoms in patients with schizophrenia.
 
 • To evaluate the magnitude of the effect of PEAR-004 as an adjunct to existing clinician-directed pharmacotherapy to reduce symptoms of schizophrenia. • To evaluate the response to treatment. • To evaluate patient adherence to antipsychotic medication. 	
 • Vital signs at baseline, day 85 or last visit. • InterSePT Scale for Suicidal Thinking-Plus (ISST-Plus) score at baseline, day 29, day 57, day 85, and day 115 or last visit. • Change on the World Health Organization Quality of Life (WHOQOLBREF) scale from baseline to day 29, day 57, and day 85 or last visit. • Change in the Beck Depression Inventory, Second Edition (BDI-II) total score from baseline to day 29, day 57, and day 85 or last visit. • Percentage change in PANSS score (within assigned group) from baseline to day 29, day 57, and day 85 or last visit. • Proportion of responders, defined as a reduction of at least 20% at day 85 or last visit in total PANSS score relative to baseline. • Change in antipsychotic pharmacotherapy use as measured by the Brief Medication Questionnaire (BMQ) at day 29, day 57, and day 85 or last visit.
--	--

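### The 20% responder endpoint lets a score from another visit stand in for a missing day-85 PANSS, so unequal dropout can bias the responder difference whenever response changes over visits or dropout is related to outcome

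*Protocol*

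**What the plan says.** Protocol Table 2-1 lists, as a secondary endpoint, "Proportion of responders, defined as a reduction of at least 20% at day 85 or last visit in total PANSS score relative to baseline". SAP 1.3.2 carries the same definition: "Proportion of responders, defined as a reduction of at least 20% at day 85 or last visit in total PANSS score".

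PANSS is scheduled at days 29, 57 and 85 during treatment and again at day 115 (Protocol Table 8-1). Protocol section 8 adds an exit visit: "Subjects who prematurely discontinue the study for any reason should be scheduled for a visit as soon as possible", with the final-visit assessments. The footnote to Table 8-1 says of the starred end-of-study items, which include PANSS: "These assessments are also to be conducted for subjects who discontinue study treatment". Protocol 9.1.1 asks subjects who stop treatment to come back, "especially the day 85 and EOS (day 115) visits", and 9.1.3 encourages them to remain in the trial.

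The FAS needs a baseline and at least one post-randomization observation (Protocol 12.1, SAP section 4).

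For change in total PANSS, Protocol 12.4.3 states: "The primary MMRM model implicitly imputes missing data under a missing at random (MAR) assumption". LOCF is confined to a supportive role in 12.4.4.2: "These results will only be used to aid in the interpretation of the results from the primary analysis".

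**The concern.** For the endpoints analysed by the mixed model for repeated measures (MMRM), the last-visit wording does little, because the model estimates the day-85 mean without carrying any score forward. For a yes/no outcome, the same wording fixes each subject's status. A subject whose only post-baseline PANSS is at day 29 enters the 12-week responder rate on a four-week score. On the same scale, the plan thus uses MAR for the primary result, keeps LOCF supportive, and makes LOCF the definition of response.

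The carried score can mislead in two ways. If the response rate differs between visits, an arm with more missing day-85 scores is measured, on average, at a different time from the other arm. If dropout depends on how subjects are doing, the carried scores are also a selected group. Either way, a responder difference becomes partly a dropout difference. Unequal dropout is possible here. Retention is a primary objective, subjects and site staff may know the assignment (Protocol Table 6-1), and the sham shows only notifications and a timer (Protocol 4.3).

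The last visit is also undefined. Read literally, it could be day 115, after the 12-week treatment period.

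**Working it through.** **Plan's own figures.** The documents give none for the responder endpoint. The nearest is Table 12-1 for mean PANSS change. Power = Φ(Δ / (SD·√(2/n)) − 1.645) with n = 51 per arm and SD = 16. For Δ = 8: 8 / (16 × 0.198) = 2.525; 2.525 − 1.645 = 0.880; Φ = 81.1%, against 81% stated. For Δ = 4, 6 and 10 the formula gives 35.1%, 59.8% and 93.5%, against 35%, 59% and 93%. The sample size reproduces and is not in dispute.

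**Inputs for the responder check.** From the documents: 51 per arm, one-sided 0.05, visits at days 29, 57 and 85. Assumed, because the documents do not give them: response rates by visit, dropout rates, last scores of dropouts split evenly between day 29 and day 57, and a pooled two-proportion z-test evaluated by exact binomial enumeration.

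**Formula.** With response rates p29, p57, p85 and dropout share d, the rate under the last-visit rule is

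p29·d/2 + p57·d/2 + p85·(1 − d).

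If both arms share the same response rates, the spurious gap in favour of the arm with less dropout is

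(d_high − d_low) × [p85 − (p29 + p57)/2].

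**No true difference, dropout 30% versus 10%** (d_high − d_low = 0.20):

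| Response at days 29/57/85 | Calculation | Gap (points) | Chance of a false finding for the arm with less dropout |
|---|---|---|---|
| flat 30/30/30% | 0.20 × 0 | 0 | 5.2% |
| 20/25/30% | 0.20 × (0.30 − 0.225) | 1.5 | 7.2% |
| 15/25/35% | 0.20 × (0.35 − 0.20) | 3.0 | 9.7% |
| 10/25/45% | 0.20 × (0.45 − 0.175) | 5.5 | 13.5% |
| waning 40/35/30% | 0.20 × (0.30 − 0.375) | −1.5 | 3.7% |

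At 40% versus 10%, the third row becomes 0.30 × 0.15 = 4.5 points (12.8%) and the fourth 0.30 × 0.275 = 8.3 points (21.1%).

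**True difference, 50% versus 30% at day 85.** Assumed paths are 20/35/50% for PEAR-004 and 10/20/30% for sham. With no dropout the gap is 20 points and power 66%.
- Dropout 30% PEAR-004, 10% sham: 0.20×0.15 + 0.35×0.15 + 0.50×0.70 = 43.25%; 0.10×0.05 + 0.20×0.05 + 0.30×0.90 = 28.5%; gap 14.75 points, power 47%.
- Reversed, 10% and 30%: 47.75% − 25.5% = 22.25 points, power 76%.
- 20% in both arms: 45.5% − 27.0% = 18.5 points, power 62%.

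**Simulation of PANSS itself.** Assumptions: baseline mean 80 (SD 12, kept above 60); change SD 11/14/16; correlations 0.6 to 0.75; mean change −4/−7/−9 in sham and −7.5/−13/−17 in PEAR-004 with an effect. With no effect and dropout 10% versus 30%, the last-visit gap is about 2.5 points and one-sided error about 9%. With the 8-point effect, the true 19-point gap falls to about 14 at 30% PEAR-004 versus 10% sham dropout, and rises to about 21 with dropout reversed.

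**Informative dropout.** In a second simulation (change SD 12/14/16, gradual improvement, no effect, 30% versus 10%), the gap is 3.0 points with random dropout, 4.1 if subjects doing worse leave, and 2.1 if those doing better leave.

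**Alternatives.** Counting missing as non-response gives a gap of p85 × (d_high − d_low) when there is no true difference: 0.35 × 0.20 = 7.0 points in the middle case, against 3.0 for last visit. In the PANSS simulation it gives about 6.4 points and about 18% error. Multiple imputation of day-85 PANSS from treatment, baseline and earlier visits gives a gap of about zero when data are MAR. With 30% dropout in both arms, power is about 55% under either imputation or last visit. With 30% PEAR-004 versus 10% sham it is about 58% against 42%.

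**The case against.** The best defence has four parts.

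First, the last-visit phrase is attached to nearly every endpoint in Table 2-1, including the primary, where the model overrides it. The responder analysis might do the same. Protocol 12.5.1 has a redacted block just after the percentage-change paragraph, where a responder method could sit. This stands in part. A reader might infer that the plan has no rule for missing response, and the visible text does not support that for the protocol. SAP 6.2.2 does not mention responders, but the definition is unredacted in both documents. A hidden day-85 rule would contradict it and need reconciling.

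Second, a reader might infer that everyone without a day-85 PANSS is classed on week 4 or week 8. The documents do not say so. There is an exit visit, PANSS is collected at day 115, and subjects who stop the app are asked back for day 85. Subjects with no post-baseline PANSS are outside the FAS. The calculations above include no exit visit or retrieved day-85 score, so they probably overstate the bias.

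Third, a reader might infer that unequal dropout alone is enough. It is not: the flat row gives zero and the waning row reverses the sign. Nor do the documents say that PANSS is expected to keep falling or that retention is expected to differ. The objective is only to evaluate retention, and the log-rank alternative has no direction.

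Fourth, the effect is small. A gap of 2.5 points is about one subject in 51, against a sampling standard deviation of about 9 points for the difference. That is true, and it limits the importance of the point. It does not justify keeping an avoidable bias.

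**Conclusion.** The point holds as a modest, avoidable bias in one secondary endpoint. Followed as written, the definition is LOCF on a binary outcome, at odds with how the plan treats the same scale elsewhere. When response changes over visits or dropout is related to outcome, unequal dropout can move the responder difference in either direction. Under assumed improvement and 30% versus 10% dropout, the spurious gap is about 1.5 to 5.5 points, and a true gap of about 19 points can fall to about 14. Those figures rest on response paths, dropout rates and a test that the documents do not give.

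The primary MMRM contrast is not affected. Follow-up of subjects who stop treatment reduces the problem to the extent that it yields day-85 scores. It would be tempting to claim that the change restores the power of complete data. It does not: with equal dropout in both arms the gain is negligible. The benefit is mainly lower bias when dropout is unequal. This should be changed, but it does not threaten the trial's main conclusion.

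**What to change.** In Protocol Table 2-1 and SAP 1.3.2, define response as a fall of at least 20% from baseline in total PANSS at day 85. Then, in the SAP:

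- Where day-85 PANSS is missing, impute it by multiple imputation under the same MAR model as the primary analysis (treatment, baseline, earlier visits), derive response from the imputed score, and combine by Rubin's rules.
- Keep the last-visit version as a supportive table only, with the last visit defined as the last PANSS up to day 85.
- If a missing-equals-non-responder analysis is shown, label it as sensitive to unequal dropout. Its null gap is about 6 to 7 points in the scenario where last visit gives about 2.5 to 3.
- Reconcile the wording with any responder rule in the redacted part of Protocol 12.5.1.

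The cost is a definition in two documents and one extra program before database lock. Imputed responder counts will not be whole numbers.
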